5.4 Organ at risk delineation

For treatment planning purposes, contouring of normal structures will be performed on the “average” CT dataset. For assessment of OAR motion, the data analysis will involve re-contouring at each phase of the respiratory cycle.

5.4.1 Esophagus

The full thickness of the esophagus will be contoured using oral contrast media (Esophocat) in conjunction with mediastinal windowing on CT. Sagittal and coronal reconstructions will be used to verify the 3-dimensional coherence of the esophageal volume. The esophageal volume should (at minimum) include the esophagus from the top of the VB one level above the target and continuing on every CT slice to the bottom of the VB one level below the target. For treatment planning, oral contrast in the esophagus will be assigned the density of soft tissue to minimize any alteration of the calculated dose distribution. For additional analysis (but not for dose constraint purposes) the contrast media will be used to create regions of interest corresponding to the lumen (contrast media) and organ wall (esophagus volume – lumen)

5.4.2 Other organs at risk

Other organs at risk that may be contoured include: spinal cord, lungs, liver, kidneys, larynx/pharynx, trachea, and skin. These structures will be contoured as per the guidelines established in RTOG 0631 (12).

5.5 Dose constraints

5.5.1 Esophageal dose constraints

The esophageal dose constraints for the protocol are summarized in Table 3. In stage 1, focusing on use of the fiducial system, patients dispositioned to undergo single and multi-fraction treatments will be enrolled, using our current practice guidelines for esophageal dose

constraints. For single fraction treatments, 5 cc of the esophageal volume must receive less than 12 Gy and the maximum dose (defined as that delivered to less than 0.01 cc of the esophageal volume) must not exceed 16 Gy. For 3 fraction treatments, 5 cc of the esophageal volume must receive less than 15 Gy and the maximum dose received must not exceed 21 Gy. The dose to 1cc of esophageal volume will be recommended, but not required, to be under 14 and 17 Gy respectively.

In stage 2 of the protocol, only patients receiving single fraction treatment will be eligible. Group 3 patients will be planned with constraints of 14.5 and 19 Gy to 5cc and 0.01 cc's respectively, with a recommended dose of 17 Gy as a 1 cc constraint. These dose constraints represent published guidelines issued by other groups with expertise in stereotactic radiation treatment, and will be prospectively validated in our system. Once Group 3 accrual and monitoring has been completed, we will enroll patients to Group 4, with 5 cc and 0.01 cc constraints of 18 Gy and 22 Gy and a recommended 1cc limitation to 20 Gy. The maximum esophageal dose in this group compares favorably to the maximum dose allowed on RTOG 0813 (when converted to 2 Gy fraction equivalents using the linear-quadratic model, the Group 4 Dmax is 80% of the dose allowed on this multicenter protocol).

The doses constraints chosen for Group 4 have clinical relevance for patients undergoing spine SBRT for metastatic renal cell carcinoma – these tumors are prescribed to receive a single fraction dose of 24 Gy, yet, for lesions adjacent to the esophagus, tumor coverage must sometimes be compromised to respect our current esophageal maximum of 16 Gy. Thus, prospective validation of higher esophageal tolerances would allow improved tumor coverage, with expected improvement in tumor control.

Table 3. Esophageal Dose Constraints for single fraction treatments (Gy).

* = recommended, but not mandated.

Stage	Patient Group	< 5cc	<1cc*	<0.01 cc
Stage 1	Group 1	12	14	16
	Group 2	12	14	16
Stage 2	Group 3	14.5	17	19
	Group 4	18	20	22

5.5.2 Non-esophageal dose constraints

With the exception of esophageal dose, treatment planning will be based on our group's current standards for organ-at-risk (OAR) dose constraints; however the final target volume and treatment plan will be at the discretion of the attending physician. Treatment planning will be carried out using the "average" image stack if a 4D CT data set is used.

5.6 Set-up verification

On the day of treatment, patients will first be set up on the treatment table as per our standard practice. Once the patient has been positioned by the treatment team, the ExacTrac software will calculate couch correction based on bony fusion of kV images with the treatment planning CT scan. These couch corrections will be transmitted to the patient couch, and the ExacTrac software will re-verify. Next, the cone beam CT will be used to perform a verification scan. In-house 3D-3D matching software will be used to verify the position of the final treatment isocenter. This procedure represents our current clinical practice, and is unchanged for this protocol. The cone beam CT dataset will also provide independent, 6-dimensional information on the accuracy of the calculated couch correction.

6.0 Evaluation During Study

Following treatment, patients will be evaluated in follow-up visits at months, 3 (+/- 2 weeks), 6 (+/- 4 weeks), 9 (+/- 4 weeks), 12 (+/- 8 weeks), 18 (+/- 8 weeks) 24 (+/- 8 weeks), and annually thereafter. Additional follow-up visits may be scheduled as needed in the judgment of the attending physician.

Toxicity will be monitored and recorded as per the NCI Common Terminology Criteria for Adverse Events (CTACE) version 4.0. Specific esophageal toxicity endpoints to be monitored include: dyspepsia, dysphagia, fistula, hemorrhage, necrosis, obstruction, pain, perforation, stenosis, ulcer, varices and esophagitis. Additional workup of esophageal symptoms (e.g., endoscopy, swallowing evaluation) will be at the discretion of the treating physician. Additional systemic agents or subsequent radiation therapy to the esophagus in the course of treatment will be recorded at each follow-up.

While acute esophagitis is not the primary parameter to be monitored, this protocol will also assess transient effects of spinal SBRT. Patients will complete MD Anderson Symptom Inventory (MDASI), with inclusion of the MDASI lung module, which has been previously used to assess acute esophagitis during thoracic chemoradiation therapy (41), at baseline and then weekly for four weeks following treatment. The MDASI spine module will also be incorporated into the questionnaire. Patients in Groups 1, 3, and 4 will also be asked to score use of antacids or anti-reflux medications at baseline and weekly for four weeks following treatment. Changes in patient medications (e.g. prescription of corticosteroids) at the time of spinal radiation therapy will be recorded.

7.0 Criteria for Response

Radiographic Treatment Failures

Primarily, this protocol is one of technology verification and toxicity monitoring. As such, tumor response will not be a primary data point. However, patients will be monitored at each follow-up visit, with MRI of the spine performed at each follow-up time point during the first year. Treated lesions will be classified as progressive (defined as $> 25\%$ increased volume), stable (defined as radiographically unchanged), or smaller, and spinal tumor progression-free survival (PFS) will be calculated.

Pre-Specified Dosimetric Analysis

Assessment of dose delivered to esophagus will include analysis of several dosimetric parameters, including:

- 1) Maximum dose (Dmax) = the highest dose received by 0.01 cc volume of esophagus
- 2) Dose to 5 cc (D5cc) = the highest dose received by a 5 cc volume of esophagus
- 3) Central lumen dose = the dose delivered to the centroid of the esophageal contour as calculated on a given axial slice.
- 4) Full thickness dose = dose delivered to the full thickness of the esophageal wall as calculated on a given axial slice

Any adverse esophageal events will be correlated with these parameters to determine the most appropriate definition of esophageal dose constraints.

We will use descriptive statistics to summarize the demographic and clinical characteristics of patients enrolled in this study. We will similarly summarize Dmax, D5cc, central lumen dose, and full thickness dose for each patient group (defined above).

We will use the methods of Bland and Altman (43) to compare the positioning of the isocenter with respect to 6 directional orientations (superior-inferior, anterior-posterior, lateral-medial, pitch, roll, and yaw) using the implanted fiducial markers and using our standard practice for each patient group. We will similarly compare the 3-dimensional distance from the isocenter as calculated using the implanted fiducial markers and using our standard practice. We will also estimate these paired differences (fiducial – standard practice) with 95% confidence intervals, and we will estimate with 95% confidence intervals the correlation between the measures made using the fiducial markers and those made using standard practice. We will similarly analyze Dmax, D5cc, central lumen dose, and full thickness dose for each patient group.

We will tabulate adverse events by grade for each patient group.

Sample Size

We will test whether the paired difference (fiducial – standard practice) in 3-dimensional distance from the isocenter is significantly different from 0. A sample size of 10 patients in each patient group will give us 80% power to detect an effect size of 1 standard deviation with a 2-sided significance level of 0.05. A sample size of 10 patients will also give us 82% power to

detect a correlation between the 2 methods of estimating the position of the isocenter of at least 0.80 using a 2-sided significance level of 0.05. These sample size calculations were performed with nQuery Advisor ® 7.0 (Copyright © 1995-2007, Statistical Solutions, Saugus, MA).

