2.1 Characterizing geometric uncertainty in treatment delivery

For spinal SBRT, accuracy in patient positioning is the cornerstone of providing safe and high quality treatment. Previous work from our institution underscored the importance of precise patient set-up, permuting delivered treatment plans to account for potential setup error, and demonstrating that a 2mm translational error can lead to >5% loss of tumor coverage, and greater than 25% increase in the maximal dose to the organs at risk (16).

Our current practice employs the Brain Lab ExacTrac targeting system (17, 18) which uses floor-mounted kV imagers to acquire a pair of orthogonal oblique films, which are used

(sometimes in conjunction with external locator devices) by the system software to compare the patient's position relative to the treatment planning dataset on the basis of bony anatomy. Based on this software fusion, the system calculates the required couch shifts to achieve optimal patient alignment, which are executed through a robotic couch system. Next, the coordinates of the final isocenter are verified using a CT-on-rails system to acquire a three-dimensional dataset. In-house software (19) is used to perform a 3D-3D fusion of the datasets, which then allows computation of the deviation from the planning CT, with tolerances for translation and rotational error of 1 mm and 2 degrees, respectively. Our current practice thus uses the ExacTrac system software to calculate the necessary couch corrections based on algorithmic alignment of bony anatomy alone. However, the ExacTrac software also has the capability calculate patient position based on implanted fiducial markers, provided that the markers are present at the time of CT simulation. Based on our extensive experience with the ExacTrac system, we observe that the bony fusion based calculations excel at detecting translational set-up errors, but can yield discrepancies in assessing rotational error (roll, pitch, yaw). We hypothesize that the addition of implanted fiducials will improve setup accuracy, particularly with regard to rotational error.

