2.3 Incorporation of lessons learned to date

As of this revision (Version 8), we have accrued 7 patients into Stage 1 of the protocol (five in group 1, and two in group 2). In reviewing our data to date, we conclude that the residual alignment error as calculated using either the bony fusion algorithm or implanted fiducial methods are in good agreement, with no significant difference between the methods (Figure 1).

[figure not shown]

Figure 1: Left panel - Examining the differences in the calculated error in each dimension using both fusion and fiducials reveals good agreement (average difference near zero). Right panel - RMS analysis demonstrates no statistical or clinically meaningful difference.

Extending our analysis, we have performed offline 6D fusions of the CT-on-rails-datasets with the simulation data sets, and conclude that fiducials are no better than the bony fusion algorithm for correcting rotational error (Figure 2).

[figure not shown]

Figure 2: Using offline 6 dimensional fusion, an accurate assessment of residual rotational error can be performed. RMS analysis demonstrates no significant difference in performance between the two approaches.

An additional development has been the migration of our spinal SBRT treatments to a new linear accelerator, with upgraded capabilities (e.g. 6D robotic couch correction, cone-beam CT, and improved fusion algorithm). These new capabilities will further improve the overall accuracy of patient setup with respect to rotational error. As we have demonstrated that any difference between the fusion approach and the fiducial approach has thus far been too small to detect, we believe that the improved platform would further close the hypothetical gap between the approaches, and that we will not be able to observe it.

Thus, going forward, we will:

- Remove the fiducial component from the protocol

- Prospectively enroll additional patients (without the need for fiducials) to characterize the accuracy of the new treatment platform, including a group of patients with tumors in the cervicothoracic junction (who were not originally included because of challenges with fiducial placement)
- Perform a retrospective study of setup accuracy in patients with cervicothoracic junction tumors as historical controls

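### The fiducial comparison is planned per patient group, but only 5 and 2 patients have fiducials: the Group 2 results are degenerate, and no confidence interval is planned for the limits of agreement

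*Combined protocol and SAP*

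**What the plan says.** Section 8.0, Analysis, names the agreement method by citation: "We will use the methods of Bland and Altman (43) to compare the positioning of the isocenter with respect to 6 directional orientations". The comparison is made "using the implanted fiducial markers and using our standard practice for each patient group", and the 3-dimensional distance from the isocenter is treated likewise. The section then asks for 95% confidence intervals for the paired differences (fiducial minus standard practice) and for the correlation between the two sets of measurements. It gives no multiplier for limits of agreement, no confidence interval for them, and no unit of analysis.

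The Sample Size text assumes ten patients in every group: "A sample size of 10 patients in each patient group will give us 80% power to detect an effect size of 1 standard deviation". The test is two-sided at the 0.05 level. It also claims 82% power to "detect a correlation between the 2 methods of estimating the position of the isocenter of at least 0.80".

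Actual numbers are given in section 2.3: "we have accrued 7 patients into Stage 1 of the protocol (five in group 1, and two in group 2". The same section removes fiducials from the protocol. Section 5.1 closes Groups 1 and 2 and opens Groups 5 to 7, ten patients each, without implanted markers. Section 5.5.1 admits both single-fraction and multi-fraction patients to Stage 1.

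**The concern.** The per-group instruction was written for groups of ten. The only groups that can supply fiducial pairs have five and two patients. Splitting seven patients in this way leaves one small analysis and one that cannot inform.

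Two patients with one pair each give a correlation fixed in advance at +1 or −1 and a confidence interval for the mean too wide to interpret. Limits of agreement from five or two differences are also very uncertain, because both the mean and the SD are estimated, and the plan attaches no interval to show it. Section 2.3 already reports good agreement between the methods. Limits printed without intervals could make that conclusion look firmer than seven patients allow.

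**Working it through.** **Inputs.** Planned n = 10 per group, effect 1 SD, two-sided alpha 0.05, correlation 0.80 (section 8.0). Actual n = 5 in Group 1 and 2 in Group 2, so 7 pooled (section 2.3). Assumptions: normal, independent differences, one per patient. For coverage only, limits of the form mean ± 1.96 SD.

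**1. The plan's own figures.** A paired t-test with n = 10, 9 degrees of freedom and noncentrality √10 has power 0.803, against the stated 80%. For the correlation, Φ(atanh(0.80) × √7 − 1.96) = Φ(1.0986 × 2.6458 − 1.96) = Φ(0.947) = 0.828, against the stated 82%. Both reproduce at n = 10. At the actual numbers, the same paired t-test has power of about 40% (n = 5), 9% (n = 2) and 60% (n = 7).

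**2. Confidence interval for the mean difference.** The half-width is t(0.975, n−1)/√n, in units of the SD of the differences analysed.

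- n = 2: 12.706/1.414 = 8.98 SD
- n = 5: 2.776/2.236 = 1.24 SD
- n = 7: 2.447/2.646 = 0.92 SD

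**3. Correlation in Group 2.** Two distinct points always lie on a straight line, so r is +1 or −1 (barring ties). The Fisher standard error is 1/√(n − 3), which does not exist at n = 2.

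**4. Average coverage of mean ± 1.96 SD for a new difference.** This is P(|t with n−1 df| < 1.96/√(1 + 1/n)). The last column is the multiplier that gives 95% on average, t(0.975, n−1) × √(1 + 1/n).

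| n | Average coverage | 10th percentile of realised coverage | Multiplier for 95% |
|---|---|---|---|
| 2 (Group 2) | 64.4% | 14% | 15.6 |
| 5 (Group 1) | 85.2% | 63% | 3.04 |
| 7 (pooled) | 88.4% | 73% | 2.62 |

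Simulation with 200,000 samples per n gave average coverages of 64.4%, 85.2% and 88.3%. With a multiplier of 2 instead of 1.96, the formula gives 65.0%, 85.8% and 88.9%.

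**5. Confidence interval for one limit of agreement.** The approximate half-width is t(0.975, n−1) × √(1/n + 1.96²/(2(n−1))) SD.

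- n = 2: 12.706 × √(0.500 + 1.921) = 19.8 SD
- n = 5: 2.776 × √(0.200 + 0.480) = 2.29 SD
- n = 7: 2.447 × √(0.143 + 0.320) = 1.66 SD

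**The case against.** The strongest reply is that the plan only cites a method. It writes no multiplier, so under-coverage is a property of a formula that the text does not contain, and the cited paper may itself supply intervals for the limits. That stands: the 85% and 64% figures are conditional on the conventional form. What the text does show is that intervals are requested for two quantities and not for the limits. The Group 2 degeneracy does not depend on any multiplier.

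Multi-fraction patients are admitted, so there may be more than 5 and 2 pairs. That also stands. Repeated pairs would change the coverage figures and the Group 2 results, but they are correlated within a patient, so the unit of analysis would still have to be stated.

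Limits that estimate population quantiles and limits that predict a new difference are different targets. The t-based multiplier is therefore one option and not the only correct one.

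Finally, fiducials have already been dropped, so nothing here changes a design decision. That is true, and it limits the weight of the point to how seven patients are reported.

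A reader might infer more than the documents support:

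- That the shortfall at ten patients per group (90.6% coverage under the same assumptions) is what this trial faces. No current fiducial comparison has ten patients; Groups 5 to 7 have no markers.
- That agreement on the new treatment platform will be overstated. The planned comparison needs fiducials and cannot be run there.
- That limits will be judged against the "tolerances for translation and rotational error of 1 mm and 2 degrees" in section 2.1. Those are set-up tolerances for deviation from the planning CT. No section makes them an acceptance margin for fiducial-minus-standard differences.
- That the error always favours agreement. It does so on average only. In the simulation, 1.96 SD limits covered less than 95% in 67% of samples at n = 5 and 75% at n = 2, so in the other 33% and 25% they covered at least 95%.

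**Conclusion.** The point holds for the fiducial comparison in closed Groups 1 and 2, and only there. With one pair per patient, the Group 2 analysis carries almost no information: a mean-difference interval of ±8.98 SD and a correlation that can only be +1 or −1. Group 1 alone gives ±1.24 SD, while the seven pooled give ±0.92 SD. If conventional limits are used, their average coverage would be about 85% in Group 1 and 64% in Group 2.

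These figures rest on normal differences, one per patient, and the counts in section 2.3 being final. The Safety text in section 8.0 still lets Group 2 accrual continue, which conflicts with the closure in section 5.1. The two should be reconciled, since the counts depend on it. The gain from pooling further assumes that thoracic and lumbar patients share a similar mean and SD of the difference.

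**What to change.** In section 8.0, Analysis, for the fiducial comparison only:

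1. Replace the per-group instruction with one pooled analysis of the 7 patients in Groups 1 and 2, with spinal level shown by symbol on each Bland-Altman plot.
2. State the unit of analysis: one value per patient, or a model that allows for repeated fractions within a patient.
3. Report each limit of agreement with a 95% confidence interval, or give t-based limits (multiplier 2.62 at n = 7 with one value per patient), and say which form is used.
4. Drop the separate Group 2 correlation.

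The cost is a few sentences of plan wording and no new data. The reported limits will look wider: t-based limits at n = 7 are 2.62/1.96 = 1.33 times the conventional ones. Pooling would hide a real thoracic–lumbar difference in the mean, apart from what the plot shows, and such a difference would inflate the pooled SD. With only two lumbar patients, a separate analysis could not estimate that difference usefully either.

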1.0 Objectives

- 1.1 Assess the use of implanted fiducial markers in the treatment planning and delivery workflow for frame-based spinal stereotactic body radiation therapy (spinal SBRT).
- 1.2 Characterize the six-dimensional set-up accuracy of the ExacTrac patient positioning system as applied to spinal SBRT for lesions of the thoracic and lumbar spine.
- 1.3 Establish whether the addition of implanted gold seed fiducials enhances the ability of the ExacTrac system to detect and correct patient position relative to image fusion based solely on bony anatomy.
- 1.4 Characterize the radiation dose delivered to organs at risk (OARs) when accounting for intrafraction OAR motion through the use of 4 dimensional CT simulation for treatment planning.
- 1.5 Characterize the radiation tolerance of the normal esophagus to large-fraction radiation treatment through dose constraint relaxation.

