The incorporation of implanted fiducials would thus allow us to address two important questions. Firstly, by having the ExacTrac software calculate the required couch corrections with and without consideration of the fiducial markers, we will be able to assess whether the use of implanted fiducials enhances the accuracy of the ExacTrac fusion as compared to fusion based on bony anatomy alone, verified by CT-on-rails. Secondly, the presence of fiducial markers will allow a more accurate comparison of the verification CT dataset with the planning CT, thus allowing us to assess whether our current practice of final 3D-3D verification is necessary.

The use of implanted fiducial markers has been well established in other radiation therapy platforms, including use in image guided radiation therapy for prostate cancer (20) or SBRT for liver disease (21). With respect to spinal SBRT, the Cyberknife platform for stereotactic treatment delivery uses implanted fiducial markers as part of a frameless treatment delivery system (10, 22).

While implanted gold seeds are commonly and safely used for multiple indications, and frequently utilized in clinical spinal SBRT practice, the use of implanted fiducials for patient setup analysis in frame-based spinal SBRT has not been well reported in the clinical literature. A pilot study at the University of Arizona investigated their use in three patients treated with the Novalis Body system, finding the use of implanted fiducials provided superior set-up as compared to bony fusion alone (23). A limitation to this study was the lack of final 3D verification of the type that our CT-on-rails system can provide – thus, the comparisons between bony fusion and marker fusion ultimately derived from ExacTrac software based calculation of true fiducial position – not an independent verification scan.

Thus, the most basic goal of this protocol is to incorporate a well-established practice (implanted gold fiducials) into our treatment delivery platform for spinal SBRT, allowing us to validate the robustness of our system, and, with increased confidence in the accuracy of treatment delivery, enhance clinical decision making.

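### Section 8 compares the fiducial reading with an undefined standard-practice reading and names no CT reference, so as written it measures agreement and does not answer Objective 1.3

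*Combined protocol and SAP*

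**What the plan says.** Objective 1.3 (Section 1.0) is to find out whether adding fiducials "enhances the ability of the ExacTrac system to detect and correct patient position relative to image fusion based solely on bony anatomy". Section 2.1 names the yardstick. The study is to assess whether fiducial use "enhances the accuracy of the ExacTrac fusion as compared to fusion based on bony anatomy alone, verified by CT-on-rails". The same section faults an earlier three-patient pilot study because its comparison was "ultimately derived from ExacTrac software based calculation of true fiducial position", with no independent scan.

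Section 8.0 (Analysis) plans Bland-Altman comparisons in six directions, a comparison of 3D distance, paired differences with 95% confidence intervals, and a correlation. Each sets the fiducial result against standard practice. The 3D comparison reads: "We will similarly compare the 3-dimensional distance from the isocenter as calculated using the implanted fiducial markers and using our standard practice." The Sample Size text states the test: "We will test whether the paired difference (fiducial – standard practice) in 3-dimensional distance from the isocenter is significantly different from 0." It claims 80% power for a 1 SD effect with 10 patients per group, and 82% power for a correlation of 0.80. No CT reference appears in any of these, and neither standard practice nor the distance is defined.

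Section 2.3 records 7 Stage 1 patients (5 in Group 1, 2 in Group 2), reports that "we have performed offline 6D fusions of the CT-on-rails-datasets with the simulation data sets", and removes the fiducial component. Section 5.1 closes Groups 1 and 2 and opens Groups 5-7 without fiducials. Objective 1.3 and the fiducial test remain in the text.

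**The concern.** Accuracy is closeness to the true position. A comparison of two readings shows whether they agree. Both readings contain the same true patient offset, so they can agree on average while one is much less precise, or while both share the same bias. A null result could be taken to mean that fiducials add nothing. A significant one would not, by itself, say which method is right.

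The comparator is also unclear. Sections 2.1 and 5.6 describe current practice as bony fusion followed by a 3D verification scan (Section 5.6: "This procedure represents our current clinical practice, and is unchanged for this protocol"), so standard practice in Section 8 could mean the bony reading or the CT-verified position.

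At stake is whether the fiducial data already collected are reported in a form that bears on Objective 1.3, and whether an 80% power claim stays attached to a comparison that did not reach its planned size.

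**Working it through.** **1. The plan's own figures.** Inputs from Section 8: n = 10, effect 1 SD, two-sided 0.05.

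- Paired t-test: df = 9, critical t = 2.262, noncentrality 1 × √10 = 3.162. Power is 80.3%, against 80% stated.
- Correlation, Fisher z: atanh(0.80) × √(10 − 3) = 1.0986 × 2.6458 = 2.907; 2.907 − 1.960 = 0.947; Φ(0.947) = 82.8%, against 82% stated.

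The arithmetic is sound. The question is what it applies to.

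**2. What each reading of Section 8 tests.** Let T be the true offset vector, F = T + e_F the fiducial reading and B = T + e_B the bony-fusion reading.

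| Meaning of standard practice | Quantity tested | What is missing for Objective 1.3 |
|---|---|---|
| ExacTrac bony fusion | length of F minus length of B | the CT; the limitation criticised in the pilot study |
| CT-verified position | fiducial against CT | bony fusion |
| Objective 1.3 with Section 2.1 | length of e_F minus length of e_B, errors taken against CT | nothing |

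Under the first reading, the per-axis Bland-Altman difference is e_F − e_B. With independent errors its variance is σ_F² + σ_B², which is unchanged if the two methods swap error sizes. The limits of agreement therefore cannot say which method is better. Nor does the sign of the distance difference settle it. A noisier method tends to give longer distances, but a method that detects only a fraction k < 1 of each offset gives shorter ones while being wrong by (1 − k)T.

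**3. Illustration only.** The documents give no error SDs, so all SDs here are assumed. Errors are independent and normal on each axis: bony SD 1.0 mm, fiducial SD 0.5 mm. Paired t-test, two-sided 0.05, simulated power:

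| True offset SD per axis (mm) | Difference in readings, n=10 | Difference in readings, n=7 |
|---|---|---|
| 0.3 | 75% | 53% |
| 0.5 | 58% | 39% |
| 1 | 28% | 19% |
| 2 | 11% | 9% |
| 3 | 8% | 7% |

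The test on error against CT does not depend on the offset. It has 87% power at n=10 and 66% at n=7, or 75% and 53% if the CT fusion itself has 0.3 mm error per axis.

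Two further cases, also at n=10:

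- Both methods share a 1 mm bias, with error SD 0.3 mm each and offset SD 2 mm. The readings test rejects in about 5% of trials, although both methods are wrong.
- Error SD 0.3 against 0.6 mm, offset SD 2 mm. The correlation of the two distances is about 0.89, so a high correlation does not show equal accuracy.

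**4. The sample that exists.** With the formula of step 1 and a 1 SD effect:

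| n | Critical t | Noncentrality √n | Power | 95% CI half-width, t/√n |
|---|---|---|---|---|
| 10 (planned per group) | 2.262 | 3.162 | 80.3% | 0.72 SD |
| 7 (Groups 1 and 2 pooled) | 2.447 | 2.646 | 60.0% | 0.92 SD |
| 5 (Group 1) | 2.776 | 2.236 | 40.1% | 1.24 SD |

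For 80% power the effect would have to be 1.27 SD at n=7 or 1.68 SD at n=5. Two patients (Group 2) support no useful inference. Groups 5-7 have no fiducial reading, so no paired difference exists for them.

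**The case against.** The strongest reply is that the protocol as a whole does use the CT. Section 2.1 plans CT verification of this comparison. Section 2.3 reports an offline 6D CT-on-rails analysis and concludes from it that fiducials do no better for rotation, the component in which Section 2.1 most expected a benefit. A reader might infer from Section 8 that neither method was ever scored against an independent scan. The documents do not support that, and this part of the reply stands. However, the CT-based result described is for rotation. The translational finding in Section 2.3 is given as agreement between the two calculated errors.

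A second reply is that the undefined distance in Section 8 might mean distance from a CT-verified isocenter, calculated for each method, which would be close to what is needed. That is possible but nowhere stated, and writing it in is the remedy.

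A third is that the loss of power rests on assumed SDs. This stands. Section 2.1 gives a 1 mm translational tolerance, and with residual offsets of 0.3 mm the readings test (75%) equals the CT-based test with CT noise (75%). The low figures require offsets that are large relative to that tolerance.

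Finally, fiducials have already been dropped, so nothing here alters an ongoing patient's set-up or safety monitoring. That is correct, and it limits the fix to reporting.

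**Conclusion.** The concern holds for Section 8. Under its natural readings the planned test is either agreement between two ExacTrac outputs or fiducials against CT with bony fusion missing. Neither gives the contrast in Objective 1.3. This conclusion follows from the text and needs no assumed SDs.

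A reader might go further and infer that the decision to drop fiducials was wrong, or that the planned test has only 8% power. The documents support neither. The decision also cited a CT-based rotational analysis and a new platform, and simulated power runs from 8% to 75% over assumed offset SDs of 3 to 0.3 mm.

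Redefining the outcome would not rescue the 80% figure. It belongs to 10 patients per group, and the fiducial groups closed at 5 and 2. For a 1 SD effect, power is about 40% at n=5 and 60% at n=7, so any result from these patients is descriptive.

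**What to change.** In Section 8:

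1. Replace standard practice as comparator by ExacTrac bony fusion alone.
2. Define each method's error as its calculated offset minus the offset from the independent 6D CT fusion at the same couch position. Report it per axis, for the rotations, and as 3D length.
3. Run Bland-Altman for each method against the CT, and estimate the paired difference (fiducial minus bony) in error length with a 95% confidence interval.
4. Apply this only to patients in closed Groups 1 and 2 who have matched readings, at their actual number (at most 5 and 2), and label it descriptive. Section 2.3 does not say that matched fiducial, bony and CT readings exist for all 7, so the number must be confirmed.
5. Remove the 80% and 82% power statements for the fiducial comparison, and state that Objective 1.3 and this test do not apply to Groups 5-7.
6. If any simulated power is quoted, label it illustrative.

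The cost is SAP wording and a re-analysis of existing data, with no new patients or procedures. The rotational CT fusions are reported as done; translational offsets from the same fusions may still need to be extracted. One small downside is that CT fusion error enters both methods' errors.
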